4 STUDY DESIGN

4.1 OVERALL DESIGN

This study is a multi-center, open label trial to determine the effect of AKL-T01 treatment (with AKL-X01 mobile app-based symptom tracking) on ADHD symptoms and impairments in children currently on or off stimulant.

Two hundred and three participants (203) at multiple sites will be enrolled into 2 cohorts. 130 participants will be recruited into cohort 1 and 73 participants will be recruited into cohort 2.

Cohort 1 will have been stable** on stimulant(s) for at least 30 days before baseline. At screening (at least 7 and up to 30 days before baseline), participant caregivers will be instructed to download AKL-X01 on to their smartphone. Caregivers will use AKL-X01 for tracking participants' symptoms and behaviors beginning between days -30 and -7, through day 84. During Treatment Phase 1, Days 1 through 28, participants will continue receiving stimulant and will also receive AKL-T01 treatment. During the 1-month treatment pause, Days 29 through 56, participants will continue receiving stimulant but will discontinue AKL-T01. During Treatment Phase 2, Days 57 through 84, participants will continue receiving stimulant and will also receive AKL-T01 treatment.

****Note:** Medication stability is defined as:

- Moderate response on stimulant, but still room for improvement
- Dose unchanged within past 30 days, but other doses have been tried previously without improvement
- Currently taking stimulant, but parent and/or caregiver wishes not to increase dosage for any reason
- Taking consistent stimulant dose on weekdays, but not on weekends

The hypothesis for Cohort 1 is that children receiving stimulant plus AKL-T01 treatment will improve in ADHD symptoms and impairments from Day 0 to Day 28.

Cohort 2 will have been stable without any stimulant for ≥ 30 days before baseline. At screening (at least 7 and up to 30 days before baseline), participant caregivers will be instructed to download AKL-X01 on to their smartphone. Caregivers will use AKL-X01 for tracking participant symptoms and behaviors beginning between days -30 and -7, through day 84. During Treatment Phase 1, Days 1 through 28, participants will receive AKL-T01 treatment. During the 1-month treatment pause, Days 29 through 56, participants will discontinue AKL-T01. During Treatment Phase 2, Days 57 through 84, participants will receive AKL-T01 treatment.

The hypothesis for Cohort 2 is that children receiving AKL-T01 treatment will improve in ADHD symptoms and impairments from Day 0 to Day 28.

All study visits for each participant should be completed during the same time of day (either AM or PM), to maintain consistent data collection and comparison of rater assessment results.

4.2 SCIENTIFIC RATIONALE STUDY DESIGN

The Akili-001R trial focused on randomizing participants, into the blinded study, who were not currently being prescribed a stimulant medication regimen for the treatment of ADHD. Participants were evaluated for changes in ADHD symptoms after 28 days of treatment with AKL-T01. The results of the Akili-001R trial showed a marked improvement in ADHD symptoms in participants, ages 8-12 years, who were not currently prescribed stimulant medication(s).

Four post-hoc analyses were of interest in the Akili-001R trial. First, an analysis using the Wilcoxon signed-rank test was used to determine whether the baseline and 28-day API were different within each treatment group. The resulting p-value was less than 0.0001 for AKL-T01 (EVO: Multitask) and 0.67 for placebo (EVO: Words). This result supports the observation that the mean improvement is higher for treatment than the control group. The second post-hoc analysis was to investigate whether there was an interaction between treatment and ADHD type (inattentive vs combined). There was no evidence of a clinically relevant interaction between treatment and either subgroup (all p-values were > 0.13), indicating a consistency of response irrespective of ADHD type. The third analysis using the Wilcoxon signed-rank test was used to determine whether the baseline and 28-day API were different within each treatment group for the ADHD inattentive subgroup. The resulting p-value was 0.0003 for AKL-T01 and 0.40 for placebo. This supports the observed means for the ADHD inattentive subgroup. Lastly, an alternative responder analysis was performed where a responder was a 30% reduction in API. The analysis showed there was an absolute 14.2% more responders in the treatment arm than the control arm ($p = 0.0038$).

The responder results from the Akili-001R trial led to interest in the hypothesis that AKL-T01 administered adjunctively with stimulant medication(s) in participants (ages 8 years 0 months-14 years 9 months) with ADHD may also improve the symptoms of ADHD.

4.3 JUSTIFICATION FOR DOSE

The therapeutic play regimen for the current study (typically 25 minutes per day; 5 days per week; 4 weeks) was established based on previous work with AKL-T01 digital treatment. Specifically, a recent pivotal trial of AKL-T01 demonstrated that this regimen resulted in significant improvements in TOVA API scores in a sample of children with similar characteristics as proposed in this study. The mean compliance for this regimen is 86% (STARS-ADHD).

4.4 END OF STUDY DEFINITION

A participant is considered to have completed the study if he or she has completed all phases of the study including the last visit, at Day 84.

5 STUDY POPULATION

5.1 INCLUSION CRITERIA

In order to be eligible to participate in this study, an individual must meet all the following criteria:

- 1) Male or female, ages 8 years 0 months to 14 years 9 months (inclusive), at the time of parental informed consent.
- 2) Confirmed ADHD diagnosis (primarily inattentive or combined subtype), at Screening based on DSM-V criteria and established via the MINI-KID administered by a trained clinician.
Note: Co-morbid diagnoses on the MINI-KID are acceptable provided that ADHD is the primary diagnosis and the co-morbid diagnoses will not confound study data (per the Investigator's judgment and documented in source note).
- 3) Currently experiencing sub-optimal treatment of ADHD, based upon results of Clinical Global Impression-Severity score.
- 4) Impairment Rating Scale (Parent Report) score of ≥ 3 , for #8 Overall Impairment, at Screening.
- 5) Ability to follow written and verbal instructions (English), as assessed by the PI and/or study coordinator.
- 6) Estimated IQ score ≥ 80 as assessed by the Kaufmann Brief Intelligence Test, Second Edition (KBIT-II). KBIT assessment performed within 12 months at site prior to screening visit can be used for this study and is not required to be repeated, as long as assessment documentation is available and filed with participant source.
- 7) Ability to comply with all testing, requirements, study procedures, and availability for the duration of the study.
- 8) Provision of signed and dated parental informed consent form and assent form.
- 9) Participant's parent and/or caregiver has access to any of the following Apple™ or Android™ smart phone and/or mobile devices (for accessing AKL-X01 application): Apple iPhone 6, 6+, 7, 8, 10; Android Samsung Galaxy S7, S7 Edge, S8, S8+, S9, S9+; Android Samsung Note 8; Android LG G6, G7, V30, K20. Apple mobile devices must be running iOS 11.2+. Android mobile devices must be running Nougat or Marshmallow.
- 10) **For Cohort 1 (stimulant),** participant must be stable** on stimulant medication, at an approved FDA dose, for ≥ 30 days prior to enrollment (may also be one stimulant plus a booster, provided that the dose is stable and does not change throughout the course of the trial).
- ****Note:** Medication stability is defined as:
 - Moderate response on stimulant, but still room for improvement
 - Dose unchanged within past 30 days, but other doses have been tried previously without improvement
 - Currently taking stimulant, but parent and/or caregiver wishes not to increase dosage for any reason
 - Taking consistent stimulant dose on weekdays, but not on weekends
- 11) **For Cohort 2 (non-stimulant),** participant must be stable off stimulant medication for ≥ 30 days prior to enrollment.

5.2 EXCLUSION CRITERIA

An individual who meets any of the following criteria will be excluded from participation in this study:

1. Current, controlled (requiring a restricted medication) or uncontrolled, comorbid psychiatric diagnosis, based on MINI-KID and subsequent clinical interviewing, with significant symptoms including but not limited to:
 - a. post-traumatic stress disorder
 - b. psychosis
 - c. bipolar illness
 - d. autism spectrum disorder
 - e. severe obsessive-compulsive disorder
 - f. severe depressive
 - g. severe anxiety disorder
 - h. conduct disorder
 - i. other symptomatic manifestations that in the opinion of the Investigator may confound study data/assessments.

Participants with clinical history of learning disorders will be allowed to participate, provided the disorder does not impact their ability to participate in the trial based on PI judgment.

2. Participants who are currently treated with a non-stimulant medication for ADHD (i.e., atomoxetine, clonidine, guanfacine).
3. Participants diagnosed with ADHD Hyperactive-Impulsive subtype, based upon score on the MINI-KID interview.
4. Participants showing no room for improvement, or those refractory to non-intensive ADHD treatment.
5. Initiation within the last 4 weeks from the time of consent of behavioral therapy. Participants who have been in behavior therapy consistently for more than 4 weeks may participate provided their therapy frequency and intensity is unchanged during the course of the study. Participants planning on changing or initiating behavior therapy during the course of the study will be excluded.
6. Participant is currently considered a suicide risk in the opinion of the Investigator, has previously made a suicide attempt, or has a prior history of, or is currently demonstrating active suicidal ideation or self-injurious behavior as measured by C-SSRS at Screening.
7. Motor condition (e.g., physical deformity of the hands/arms; prostheses) that prevents playing the digital treatment as reported by the parent/caregiver or observed by the investigator.
8. Recent history (within the past 6 months) of suspected substance abuse or dependence
9. History of seizures (exclusive of febrile seizures), or significant motor or vocal tics, including but not limited to Tourette's Disorder)
10. Has participated in a clinical trial within 90 days prior to Screening.
11. Diagnosis of or parent-reported color blindness (Confirmed in-clinic via ICBT)
12. Uncorrected visual acuity (confirmed via ability of participant to log-in to T01 app and complete in-clinic game play, at Baseline)
13. Regular use of psychoactive drugs (non-stimulant) that in the opinion of the Investigator may confound study data/assessments.
14. Any other medical, behavioral, or developmental condition that in the opinion of the investigator may confound study data/assessments.
15. Has a sibling also enrolled/currently participating in the same study. Siblings may participate in the study sequentially, but not at the same time.
16. Has previously been randomized in a study of Akili's videogame-like digital treatment.

5.3 LIFESTYLE CONSIDERATIONS

During this study, participants and parents/caregivers will be asked to:

- Remain on an unchanged dosage of stimulant medication (and stimulant booster, if applicable) during participation in the trial, (Cohort 1).
- Refrain from beginning any treatment with medication during participation in the trial, (Cohort 2).
- Complete gameplay of AKL-T01 for 25 minutes (consecutively) per day, for 5 days each week during the treatment periods.
- Return to the in-clinic visits (Day 28 and Day 84) with the iPad Mini (and iPad charger) that was programmed with their AKL-T01 treatment. Note: On Day 28 the clinical site will return the iPad to Akili for the 1 month break period and will receive the same device from Akili in advance of Day 56 for redistribution to the participant for Treatment Phase II.

During this study, parents and/or caregivers of participants are asked to:

- Complete evaluation of the participant's ADHD symptoms daily (5 days per week) using the AKL-X01 smartphone app. Efforts should be made so that the evaluations are completed at the end of each day, to capture behavior(s) from the entire day. All parents and/or caregivers of participants (study-wide) should complete these evaluations at the same time each day.
- Return to the in-clinic visits with their smartphone and demonstrate they are using the AKL-X01 symptom tracker as described above to the study staff.

5.4 SCREEN FAILURES

Screen failures are defined as participants who consent to participate in the clinical trial but are not subsequently enrolled into the study or administered study treatment. A minimal set of information is required to ensure transparent reporting of participant screen failures, to meet the Consolidated Standards of Reporting Trials (CONSORT) publishing requirements and to respond to queries from regulatory authorities. Minimal information includes demography, screen failure details, and eligibility criteria.

5.5 STRATEGIES FOR RECRUITMENT AND RETENTION

The following strategies and tools will be utilized to recruit participants for this trial. Recruitment initiatives utilized will be up to the discretion of each individual trial site:

- Newspaper advertisements
- Radio and Television advertisements
- StudyKik website
- Recruitment flyers
- Social media advertisements (trial site initiated and/or Truventis; social media vendor)
- ADDitude Magazine
- Trial site patient databases.

The following strategies and tools will be utilized to maintain participant retention for this trial:

- Appointment reminder cards
- Clinical site contacts parents / caregivers if child isn't using AKL-T01 regularly
- Fengo compliance reminders
- AKL-T01 built-in reminders.

6 STUDY INTERVENTION

6.1 STUDY INTERVENTION(S) ADMINISTRATION

6.1.1 STUDY INTERVENTION DESCRIPTION

AKL-T01 multitasking digital treatment was designed to incorporate the fundamental features of Neuroracer into a state-of-the-art mobile video game-like platform, which deploys modern videogame graphics, engaging reward loops, and real-time adaptive mechanics to dynamically personalize difficulty based on the user's ability. AKL-T01 multitasking treatment employs perceptual discrimination attention/memory task as well as a continuous motor "driving" task. Performance on these tasks are assessed in isolation and when performed together to calculate a performance index for each individual user. A personalized multitask treatment regimen is automatically configured and delivered to the user and is optimized adaptively to increase multitasking performance. As players proceed through the treatment periodic recalibration occurs to maintain an optimal difficulty level.

AKL-T01 treatment will be loaded by the sponsor (Akili Interactive Labs) onto iPad Mini 4 tablets. The iPads are configured to minimize the participants' ability to utilize non-study related applications. Features such as browsing the internet, downloading apps, deleting apps, and messaging are restricted. The study devices are not intended to be used for any purpose other than that outlined in this protocol. Site staff will instruct participants and parents on intended and unintended use, as outlined in this protocol. The iPads, along with chargers, will be provided by the sponsor to the clinical sites. In a separate document, a list of login credentials (participant usernames and passwords) will be provided.

Participants will be assigned one iPad Mini 4 loaded with AKL-T01 and login credentials at baseline for use during Treatment Phase I. At Day 28, participants will return the study device to the clinic. On Day 56, the participant will be assigned one iPad Mini 4 with the same login credentials for Treatment Phase II.

6.2 MEASURES TO MINIMIZE BIAS

In an effort to minimize the bias of clinical raters completing subjective clinical outcome measures, every effort should be made to restrict clinical raters' access to participant compliance data reports. Sites should identify a separate staff member to receive and review participant compliance data reports.

Additionally, bias opportunities should be minimized by the removal of rater variability. Every effort should be made, throughout the course of the trial, to maintain the consistency of rating staff among participants.

Also, to minimize the unintentional bias of study data and to maintain data consistency, clinical rater assessments for each participant should be completed at the same time of day throughout the course of the study. Also, all attempts should be made to ensure that the same parent/caregiver completes

the outcome measures. Also, all attempts should be made to ensure that the same study staff administers the subjective clinical outcome measures (ADHD-RS, CGI, and IRS).

All parents and/or caregivers of participants should complete the daily Fengo app assessment five days per week, at the end of each day, to ensure that the entire day's behavior(s) are captured. All parents and/or caregivers of participants (study-wide) should complete the Fengo assessment at the same time of day each day.

All ADHD-RS, MINI-KID and IRS-Clinician clinical assessments **MUST** be completed by a trained clinician, to maintain data consistency.

6.3 STUDY INTERVENTION COMPLIANCE

AKL-T01 automatically captures gameplay compliance and uploads these data directly to a central server when connected to WiFi. The server will automatically push daily compliance emails to the clinical sites (the format of which is described in a separate document). Based on these emails, study staff can then reach out to parents/caregivers (via the preferred contact method captured in the demographic collection) to troubleshoot technical problems and/or encourage more play. The rule for compliance outreach follow:

1. Participants that fail to play any sessions of AKL-T01 over two consecutive days will be contacted to troubleshoot potential WiFi connection problems. These participants will be highlighted in yellow in the daily compliance emails.
2. Participants that fail to play at least 35 sessions of AKL-T01 over 53 days will be contacted and reminded to play more. These participants will be highlighted yellow in the daily compliance emails.
3. Participants that fail to play any sessions of AKL-T01 over 7 consecutive days will be contacted a second time and reminded to play more. These participants will be highlighted red in the daily compliance emails.
4. Participants that fail to play at least 12 sessions of AKL-T01 over 14 days will be contacted a second time and reminded to play more. These participants will be highlighted red in the daily compliance emails.

Additionally, AKL-T01 contains built-in features that remind the participant to play each day.

6.4 CONCOMITANT THERAPY

- **If the participant is enrolled into Cohort 1 (stimulant):** Stimulant medication prescribed for the treatment of ADHD symptoms, provided that the participant's dosage has been stable** for ≥ 30 days prior to Baseline. Participant's stimulant medication dosage should remain stable during the course of the trial, as much as possible. Any titrations (including switching medications) of the participant's stimulant medication during the course of their participation in the trial will be documented within the eCRFs.

****Note:** Medication stability is defined as:

- Moderate response on stimulant, but still room for improvement
- Dose unchanged within past 30 days, but other doses have been tried previously without improvement
- Taking stimulant, but parent and/or caregiver wishes not to increase dosage for any reason
- Taking consistent stimulant dose on weekdays, but not on weekends.

Note: Stimulant medication(s) are expected to be managed by non-study clinicians (unless the site PI/Sub-I is the participant's provider).

- With the exception of common over the counter (OTC) (e.g. ibuprofen, acetaminophen, non-sedating antihistamines to treat seasonal allergies) and prescription medications (e.g. antibiotics) for minor transient ailments, regular use of concomitant medications is not permitted during the study. Daily use of some medications (i.e., non-sedating antihistamines to treat seasonal allergies) may be permitted on a case-by-case basis with PI review/approval documented. Families should advise the study staff if it becomes necessary to use other types of medication. Study investigators can approve short-term use of other medications that are not anticipated to confound study assessments.
- Initiation of or significant changes in non-pharmacological treatment for ADHD is not permitted during the course of the study. Participants actively engaged in non-pharmacological treatment at Screening may be eligible if they meet all inclusion criteria and do not undergo changes to their treatment during the course of the study.

Allowed Medications:

- 1) Stimulant medication(s), including formulaic variants of amphetamines and/or methylphenidates, which are currently FDA approved for prescribed treatment of pediatric ADHD (**if participant is enrolled into Cohort 1**).
- 2) Non-sedating antihistamines
- 3) Analgesics, including acetaminophen and ibuprofen
- 4) Antibiotics required for the treatment of minor illnesses
- 5) Vitamins
- 6) Melatonin, provided that use is intermittent and not every day and is only taken at night

Prohibited Medications, taken 30 days prior to Baseline visit and throughout the duration of the trial include:

- 1) Amphetamines (**if participant is enrolled into Cohort 2**)
- 2) Methylphenidates (**if participant is enrolled into Cohort 2**)
- 3) SSRIs (e.g., fluoxetine, paroxetine)
- 4) MAOIs (monoamine oxidase inhibitors)
- 5) Mood stabilizers (e.g., lithium, valproate, quetiapine)
- 6) Antipsychotics (e.g., risperidone, olanzapine)
- 7) Anticonvulsants (e.g., phenobarbital, phenytoin, primidone)
- 8) Anticoagulants
- 9) Dextromethorphan
- 10) Halogenated anesthetics

- 11) Tricyclic antidepressants
- 12) Atomoxetine
- 13) Guanfacine
- 14) Clonidine
- 15) Phenylbutazone
- 16) Sedating antihistamines
- 17) Decongestants with stimulant properties

7 STUDY TREATMENT DISCONTINUATION AND PARTICIPANT DISCONTINUATION/WITHDRAWAL

7.1 DISCONTINUATION OF STUDY TREATMENT

Participants may withdraw at any time during the study without prejudice or be discontinued from study treatment at the discretion of the investigator if medically necessary or if any untoward effects occur. In addition, a participant may be withdrawn by the investigator (in consultation with the sponsor as necessary) if the participant is noncompliant with their assigned treatment (as described below) or otherwise violates the study plan, or for administrative and/or other safety reason.

The investigator or designee will notify the sponsor or their designee immediately when a participant has been discontinued or withdrawn from study treatment because of an adverse event. When a participant discontinues or is withdrawn from treatment before study completion, all applicable activities scheduled for the final study visit should be performed at the time of discontinuation. Any adverse events that are present at the time of discontinuation/withdrawal should be reported and followed up in accordance with the safety requirements outlined in Section 8.3 (Adverse Events).

7.2 PARTICIPANT DISCONTINUATION/WITHDRAWAL FROM THE STUDY

Participants are free to withdraw from participation in the study at any time upon request.

An investigator may discontinue or withdraw a participant from the study for the following reasons:

- Significant study treatment non-compliance, defined as <50% compliance with study treatment
- If any clinical adverse event (AE), or other medical condition or situation occurs such that continued participation in the study would not be in the best interest of the participant
- Disease progression worsening, which requires discontinuation of the study treatment
- If the participant meets an exclusion criterion (either newly developed or not previously recognized) that precludes further study participation
- Participant unable to receive AKL-T01 for 25 minutes per day, 5 days per week, as prescribed per protocol.

The reason for participant discontinuation or withdrawal from the study will be recorded on the trial's electronic Case Report Form (eCRF). Participants who sign the informed consent form and are enrolled but do not receive the study treatment will not be replaced. Participants who sign the informed consent form, and are enrolled and receive the study treatment, and subsequently withdraw, or are withdrawn or discontinued from the study, will not be replaced.

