9.3 POPULATIONS FOR ANALYSES

There are 3 populations defined for this study: intention-to-treat (ITT); per-protocol (PP); and, safety. The ITT and PP populations will be used for efficacy analyses, and the safety population will be used for the safety analysis. The success of the primary and secondary efficacy analyses will be determined within the ITT population.

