9.3.1 INTENTION-TO-TREAT (ITT)

This population is defined as any participant enrolled in the study who receives a device. In the event that a medicated participant's clinician deems it necessary to end medication treatment (or vice versa), no correction will be made to that participant's cohort. Unless otherwise indicated, the ITT population will be used for all statistical analyses, tabular summaries, and data listings.

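### Section 7.2 lets investigators withdraw children from the study for low play, inability to receive the regimen or worsening, so the ITT primary result can be selected on adherence and outcome

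*Combined protocol and SAP*

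**What the plan says.** Section 7.2 concerns leaving the study. It begins: "An investigator may discontinue or withdraw a participant from the study for the following reasons". Two of the grounds concern adherence: "Significant study treatment non-compliance, defined as <50% compliance with study treatment" and "Participant unable to receive AKL-T01 for 25 minutes per day, 5 days per week, as prescribed per protocol". A third concerns outcome: "Disease progression worsening, which requires discontinuation of the study treatment". The wording is permissive. Withdrawn children are not replaced, and the reason goes on the eCRF.

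Section 7.1 repeats the adherence ground: "a participant may be withdrawn by the investigator (in consultation with the sponsor as necessary) if the participant is noncompliant with their assigned treatment". For a child who stops before study completion it adds that "all applicable activities scheduled for the final study visit should be performed at the time of discontinuation".

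On analysis, Section 9.3.1 defines ITT broadly: "This population is defined as any participant enrolled in the study who receives a device". Section 9.3 states: "The success of the primary and secondary efficacy analyses will be determined within the ITT population". Section 9.4.2 then leaves out of the primary test any child lacking a baseline or Day 28 IRS, and Section 9.4.1 rules out imputation throughout. The Schedule of Activities allows 3 days either side of Day 28.

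**The concern.** An ITT analysis is meant to keep the children who play little or get worse. Here the protocol itself authorises their removal before the primary endpoint is measured, in an open-label trial and, for noncompliance, with possible sponsor involvement. If removed children tend to have poorer IRS changes, the mean among those who remain moves towards improvement, and the one-sample comparison with zero takes that shift as a treatment effect.

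Nothing else in the plan would correct this. There is no control arm in which the same selection would appear. The per-protocol analysis (Section 9.3.2) requires a follow-up IRS and at least 50% play, so it makes the same selection more strongly. The only other sensitivity analysis named for the primary endpoint concerns outliers.

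**Working it through.** **1. The chain in the text.** Consider a child withdrawn for worsening on Day 10.

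- The child was enrolled and received a device, so belongs to ITT (9.3.1).
- The exit assessment falls on Day 10 (7.1), outside the Day 25–31 window, and no rule treats it as a Day 28 value.
- Section 7.3 covers missed visits and lost contact, not children whom the investigator withdraws.
- With no Day 28 IRS, the child is excluded (9.4.2) and not imputed (9.4.1).

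**2. When the play ground can first be met.** Section 7.2 gives no window for the 50% figure. If it is counted against Phase 1, there are 5 × 4 = 20 episodes. A child who never plays can still reach 20 − 2 × 5 = 10 episodes, exactly 50%, after week 2. The ground can therefore first be met in week 3, before Day 28. The worsening and inability grounds have no such delay.

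**3. The plan's sample sizes (Section 9.2).** Inputs are SD 1, two-sided 5%, 90% power, and effects of 0.30 and 0.40. Using n = (SD × (z₀.₉₇₅ + z₀.₉₀)/δ)², rounded up, gives 117 and 66, as stated. For 10% dropout, 117/0.9 = 130 as stated, and 66/0.9 = 73.3, which is 74 rounded up against the stated 73. The difference is immaterial here.

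**4. False-improvement rate when the true change is 0.** Assumptions: change ~ N(0, 1), and 130 and 73 enrolled. The k children with the highest latent score are removed, where that score has correlation ρ with the change (positive means worse). Improvement is claimed if the upper 95% bound among the rest is below 0. Each cell has 200,000 simulated trials; with k = 0 the rate is 2.4–2.5%.

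| Enrolled | Removed | ρ = 0.1 | ρ = 0.3 | ρ = 0.5 |
|---|---|---|---|---|
| 130 | 6 (4.6%) | 3.2% | 5.3% | 8.6% |
| 130 | 13 (10%) | 4.0% | 9.4% | 19.5% |
| 73 | 4 (5.5%) | 3.1% | 4.8% | 7.3% |
| 73 | 7 (9.6%) | 3.5% | 6.7% | 12% |

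The mean shift is −0.030 (Cohort 1) and −0.034 (Cohort 2) in the 5% rows at ρ = 0.3, and −0.096 and −0.092 in the 10% rows at ρ = 0.5. The 10% rows are an upper case, because the plan's 10% covers dropout from every cause.

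**5. A second method.** Suppose a share d is missing with mean change +m, and the mean over all enrolled is 0. The mean among the rest is then −d·m/(1 − d). For d = 0.10 and m = 0.5 this is −0.05/0.90 = −0.056. By the noncentral t, the false-improvement rate is 8.6% (n = 117) and 6.5% (n = 66). For m from 0.25 to 1.0 it runs from 4.8% to 22.1% in Cohort 1 and from 4.1% to 14.2% in Cohort 2.

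**6. If the planned effect is seen in those who remain.**

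- About 10% removed, with no change in them: 117 × 0.30/130 = 0.27 and 66 × 0.40/73 = 0.36, against reported values of 0.30 and 0.40.
- About 5% removed, with no change in them: 124 × 0.30/130 = 0.29 and 69 × 0.40/73 = 0.38.
- Mean worsening in removed children needed to bring the overall mean to zero: 117 × 0.30/13 = 2.7 and 66 × 0.40/7 = 3.8 points at 10%; 124 × 0.30/6 = 6.2 and 69 × 0.40/4 = 6.9 points at 5%.

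**The case against.** The strongest reply is that few children would be affected before Day 28.

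- Withdrawal is optional, Section 6.3 answers low play with reminders, and Section 4.3 reports mean compliance of 86% for this regimen. The per-protocol definition excludes low players separately, which implies that some are expected to reach Day 28.
- The 50% figure might refer to both treatment phases. With 40 episodes in all, a child who plays none in Phase 1 can still reach 20, so this ground could not be met before Day 28. Even counted against 20 episodes, a child who plays the first 2 of 5 weekdays each week has the 11th miss only on Day 25, when the visit window opens.
- No clinician IRS is scheduled between baseline and Day 28, so investigators have no interim primary score on which to select. Section 6.2 asks sites to keep compliance reports from raters.
- The correlations are assumed. If the device does nothing, low play has no causal route to the IRS change; a correlation would need common causes or the worsening ground. With no correlation the rate stays near 2.5%.
- Recorded reasons allow removals to be counted by ground.

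These points stand as reasons to expect small numbers, and they limit what can be said about size. They do not close the gap. A mean compliance of 86% says nothing about the tail, and a count counted against play to date would allow removal earlier than week 3. The worsening and inability grounds do not depend on the 50% figure, and worsening is itself an outcome. Recorded reasons show that a child left but do not supply the missing Day 28 score.

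**Conclusion.** The concern holds. The plan permits removal related to adherence and outcome before Day 28, does not retain those children, and excludes them from the analysis it calls ITT. It does not require removal, and only removals before the Day 28 window affect the primary endpoint.

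The size cannot be derived from the documents. If the true change is zero, the false-improvement rate could be modestly to several times above the nominal 2.5%, depending on an unknown share and an unknown correlation. If the true effect is near the planned one, the estimate is overstated by roughly 0.01 to 0.04 points when removed children have no change, and the conclusion would not reverse under any plausible worsening. The plan should be changed because the remedy is cheap; confidence in the practical size is moderate.

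**What to change.** In Section 7.2, and in the matching noncompliance sentence of Section 7.1, make low play, inability to receive the regimen and worsening reasons to stop AKL-T01 only. State that a child who stops for one of these reasons stays in the study and attends Day 28, and Days 56 and 84, unless consent is withdrawn. In Section 7.1, record the assessment at stopping as a separate early-stop visit that does not replace the Day 28 IRS.

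The adverse-event and exclusion-criterion grounds can stay as written, which preserves safety discretion. Those grounds, and the administrative and plan-violation grounds in Section 7.1, still allow some removal, so the change narrows the route and does not close it entirely.

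The cost is wording in two sections and one eCRF visit label. The visits are already scheduled and the planned sample size does not change. A few children will be assessed off treatment, and the estimate may be slightly smaller.
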